IRAS Project ID: **227870**

11. [name] (SpR Anaesthesia)

12. [name] (ICU Clinical Fellow)

STUDY SUMMARY

STUDY OVERVIEW	
Full title	The impact of systemic pH on cardiac function and clinical outcome in the critically ill patient
Objectives	Hypothesis Titration studies in animals with normal cardiac function show that a reduction in blood pH (and presumably that of the intracellular and interstitial compartments) from the normal level of 7.40 to 7.20 is associated with a rise in cardiac output. However, when blood pH is less than 7.20, cardiac output is reduced. Similar studies in humans with or without normal cardiac function have not been done, and yet blood pH at which aggressive treatment is recommended has been set at 7.20 based solely on animal experiments. We hypothesize that a change in blood pH in humans will also affect cardiac function, but the level of blood pH at which this is observed might be similar or different in humans. In addition, the presence or absence of

Full title of the research: **The impact of systemic pH on cardiac function and clinical outcome in the critically ill patient.**

IRAS Project ID: **227870**

	
underlying cardiac disease and the type of acid-base abnormality present might modify the response of the heart to changes in blood pH.
 
Goals
 
Primary
 
 1. Assess whether there are significant changes in cardiac function associated with changes in blood pH. 2. Relate the changes in cardiac function to presence or absence of underlying cardiac disease. 
Secondary
 
 3. To establish which factors affected by blood pH have an impact on cardiac function. 4. Study the mortality of patients admitted to the Intensive Care Unit (ICU) who had continuous cardiac monitoring at any time during their admission and relate it to changes in blood pH.
Type of trial	It is not a trial
Trial design and methods	It is not a trial
Health condition(s) or problem(s) studied	It is not a trial
Target sample size	Taking into account that the primary objective of the study is to

Full title of the research: **The impact of systemic pH on cardiac function and clinical outcome in the critically ill patient.**

IRAS Project ID: **227870**

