1 INTRODUCTION

Why?

We would like to perform an analysis of the relationship between systemic pH and cardiac function and clinical outcome in critically ill patients in patients hospitalized the Intensive Care Unit.

How is it of relevance and importance to patients and public?

Studying this subject we could provide important information about the impact of systemic pH on cardiac function and clinical outcome in seriously ill patients and enable the clinician to

Full title of the research: **The impact of systemic pH on cardiac function and clinical outcome in the critically ill patient.**

IRAS Project ID: **227870**

understand the best treatment of these patients. Patients will be studied who had cardiac monitoring during their ICU admission and an acid-base metabolic disorder. We exclude those patients with cardiac history or who presented an acute coronary syndrome during ICU admission.

IT IS NOT A THERAPEUTIC STUDY. ONLY OBSERVATIONAL. NO INTERVENTIONS.

Where?

In seven different ICU's between King's College NHS Foundation Hospital and Lewisham and Greenwich NHS Trust

How?

The study will take approximately six month to collect prospectively data from each unit. The data will be extracted from the medical notes and ICU charts. No active involvement with participants.

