2 BACKGROUND AND RATIONALE

3 OBJECTIVES

Goals

Primary

1. Assess whether there are significant changes in cardiac function associated with changes in blood pH.
2. Relate the changes in cardiac function to presence or absence of underlying cardiac disease.

Secondary

3. To establish which factors affected by blood pH have an impact on cardiac function.

Full title of the research: **The impact of systemic pH on cardiac function and clinical outcome in the critically ill patient.**

IRAS Project ID: **227870**

4. Study the mortality of patients admitted to the Intensive Care Unit (ICU) who had continuous cardiac monitoring at any time during their admission and relate it to changes in blood pH.

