8 STATISTICAL METHODS

The description of quantitative variables is carried out with central tendency and dispersion indices, whether based on values (mean and standard deviation) or on ordinations (median and interquartile range) according to whether they meet normality or not, respectively. Its graphic representation is done with Histograms and Cash Diagrams. The description of categorical variables is performed with absolute and relative frequencies in percentages. Its graphic representation is done with bar charts.

The relationship between categorical variables is analyzed by comparing proportions with the Pearson Chi-square test, provided that there are less than 20% of squares in the contingency table with expected frequencies less than 5. In the case that there is more 20% of squares with expected frequencies less than 5, the Fisher's exact test is used bilaterally.

Full title of the research: **The impact of systemic pH on cardiac function and clinical outcome in the critically ill patient.**

IRAS Project ID: **227870**

The magnitude of the effect of the relationship between two binary variables has been analyzed with the Ratios of proportions or Relative Risk and with the Odds Ratio.

The relationship between a binary exposure variable and a quantitative response is analyzed with the Student-Fisher t test for independent samples if the normality condition is met. According to whether or not the equality of variances are met, the Student-Fisher t test is used for independent groups for homogeneous variances or for non-homogeneous variances, respectively. In case of not fulfilling the condition of normality, the comparison of two means is made with the non-parametric Mann-Whitney U test.

The comparison between a polytomic predictor and a quantitative response is made through the analysis of variance (ANOVA) in the case of meeting the conditions of normality and homogeneity of variances. If any of these conditions is not met, it is done with the non-parametric H test of Kruskal-Wallis. If the polytomic predictor is ordinal, the ANOVA trend test or the non-parametric Jonckheere-Terpstra trend test is also used, depending on whether normality is met or not, respectively.

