The relationship between two independent quantitative variables is evaluated with the correlation coefficient r of Pearson if normality is met, or with the nonparametric correlation coefficient ρ of Spearman if normality is not met. Its graphic representation is made with the scatter diagrams or points.

Full title of the research: **The impact of systemic pH on cardiac function and clinical outcome in the critically ill patient.**

IRAS Project ID: **227870**

Normality is assessed with the Kolmogorov-Smirnov test with the Lilliefors significance correction for large samples, or with the Shapiro-Wilks test for small samples. The equality of variances is analyzed with the Levene variance homogeneity test.

The relationship between two related quantitative variables is performed using the Student-Fisher t-test for related samples in case the normality condition is met. Otherwise, the non-parametric Wilcoxon T test is used. The relationship between two paired categorical variables is performed by the McNemar symmetry test.

The relationship between a continuous quantitative response and one or several predictors, whether binary, polytomic or quantitative, is done with Simple or Multiple Linear Regression respectively.

The polytomous predictors variables are introduced in the Linear Regression models broken down into binary indicator variables coded with respect to the first reference category.

An estimative multivariate linear regression model of the effect of the predictor Change of pH (between the lowest and highest pH) on the response Change in cardiac output (corresponding to the moments between the lowest and the highest pH) has been performed. The possible role as confounding factors of several variables on this relationship has been evaluated. A predictive multivariate model of linear regression has been performed to evaluate the factors that intervene in the Cardiac Contractility.

Full title of the research: **The impact of systemic pH on cardiac function and clinical outcome in the critically ill patient.**

IRAS Project ID: **227870**

Both the predictive and the estimative models have been carried out with the manual backward step procedure using the criterion of decreasing statistical significance to establish the order to evaluate the withdrawal or permanence of each predictor.

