In the multivariate predictive linear regression model, the criterion of statistical significance was used to decide the maintenance or withdrawal of the predictors in each step. They remain in the model if they are significant and are removed from the model if they are not significant.

In the multivariate models of linear regression, the criterion of clinical significance has been used to decide on the maintenance or withdrawal of the predictors in each step. They remain in the model if they produce a change greater than 10% in the coefficient of the predictor of interest (presence of confounding bias) and withdraw if the change is less than 10% (absence of confounding bias).

The conditions of application of the simple or multiple linear regression (linearity, independence, normality and equality of variances) are evaluated by analysing the residuals.

Values of $P < 0.05$ are considered significant. The statistical treatment has been performed the statistical package SPSS, version 18 (SPSS Inc, Chicago, IL, USA).

Full title of the research: **The impact of systemic pH on cardiac function and clinical outcome in the critically ill patient.**

IRAS Project ID: **227870**

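### The plan hypothesises that cardiac disease and acid-base type modify the response to pH, but it fits one common pH slope and has no test of modification

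*Combined protocol and SAP*

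**What the plan says.** The hypothesis (Study Summary, Objectives) is that the presence or absence of "underlying cardiac disease and the type of acid-base abnormality present might modify the response of the heart to changes in blood pH". Primary goal 2 (Section 3) is to "Relate the changes in cardiac function to presence or absence of underlying cardiac disease".

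The statistical methods are printed three times: in the Study Summary, in Section 4 and in Section 8. Each copy contains the same relevant parts:

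- One model for the pH effect: "An estimative multivariate linear regression model of the effect of the predictor Change of pH (between the lowest and highest pH"), with change in cardiac output as the response.
- The role given to other variables in that model: "The possible role as confounding factors of several variables on this relationship has been evaluated". The retention rule is "They remain in the model if they produce a change greater than 10% in the coefficient of the predictor of interest".
- A separate predictive model for contractility, with retention by significance: "They remain in the model if they are significant and are removed from the model if they are not significant".
- A generic two-group comparison: "The relationship between a binary exposure variable and a quantitative response is analyzed with the Student-Fisher t test for independent samples", with Mann-Whitney as the fallback. It is not assigned to any goal.

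No copy specifies a product term, a stratified slope or a heterogeneity test, and none names cardiac disease or acid-base type as a covariate. The Introduction adds: "We exclude those patients with cardiac history or who presented an acute coronary syndrome during ICU admission". Sections 7.1 and 7.2 do not list that exclusion, and the data form printed under Section 20 records ischaemic heart disease and heart failure.

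**The concern.** To say that a factor modifies the response to pH is to say that the slope of cardiac change on pH change differs between its levels. A common-slope model cannot show this, whatever covariates it contains. A change-in-coefficient rule asks a different question, namely whether leaving a variable out biases the common slope. A factor can change the slope strongly and still pass as no confounder. The two-group test does not fill the gap, because it compares mean cardiac change without regard to how far pH moved.

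At stake is the part of the hypothesis that distinguishes groups of patients. Followed as written, the study could report one pH effect that describes neither patients with nor patients without cardiac disease, and nothing in the analysis would reveal it.

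**Working it through.** **1. The plan's own figure.** Inputs from Section 4: two-sided alpha 5%, power 80%, N = 346. The correlation is printed as 1.5, which is impossible; 0.15 reproduces the figure.

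n = ((1.9600 + 0.8416)/atanh(0.15))² + 3 = (2.8016/0.15114)² + 3 = 346.6.

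So 346 is sized for one pooled association. It makes no allowance for comparing slopes.

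**2. What the planned model estimates.** Let D = 1 for cardiac disease, p the share with D = 1, and b0 and b1 the standardised slopes without and with disease. If D is unrelated to the pH change, the common slope is

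b = (1 - p)·b0 + p·b1,

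whether or not D is in the model as a main effect. The expected change in the coefficient on removing D is therefore about 0%. In a large simulated sample (p = 20%, slopes +0.15/-0.15) the slope was 0.0918 both without and with D.

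**3. Size of the averaging.** Neither p nor the slopes are in the documents, so these are assumptions. At p = 30% and N = 346, power of the pooled test is Φ(atanh(b)·√343 - 1.960), plus the opposite tail:

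- Slopes 0.15 and 0: b = 0.7 × 0.15 = 0.105; 0.1054 × 18.52 = 1.952; power about 50%.
- Slopes +0.15 and -0.15: b = 0.7 × 0.15 - 0.3 × 0.15 = 0.06; 0.0601 × 18.52 = 1.113; power about 20%.

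With a common slope of 0.15 it is 80%.

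**4. What the 10% rule does.** In simulations at N = 346 with slopes +0.15/-0.15, the rule kept D in 8%, 14% and 25% of runs at p = 20%, 30% and 50%. These are chance retentions. The main effect of D was significant in 5–6%. At p = 30% the rule dropped D in 94% of runs with slopes 0.15 and 0, and in 93% with +0.25/-0.25. Even when kept, D enters as a main effect and the model still has one slope.

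**5. What a product term could show at N = 346.** SE = √((1 - 0.15²)(1/n1 + 1/n2)). At p = 30%, n1 = 103.8 and n2 = 242.2, so SE = 0.116 and the 95% CI for the slope difference is ±1.96 × 0.116 = ±0.23.

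| Share with disease | Power, +0.15/-0.15 | N for 80% | Power, 0.15 vs 0 | N for 80% |
|---|---|---|---|---|
| 10% | 39.5% | 948 | 13.5% | 3,789 |
| 20% | 61.7% | 533 | 20.4% | 2,132 |
| 30% | 73.5% | 406 | 25.3% | 1,624 |
| 50% | 80.6% | 341 | 29.2% | 1,364 |

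For +0.15/-0.15 at 30%, comparing two Fisher z values gives 72% and simulation 71%. For +0.25/-0.25 at 30%, simulation (unit residual SD) gives 98%. That is a favourable case: the difference of 0.50 is large beside the 0.15 that underlies the sample size.

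**The case against.** **Goal 2 can be read literally.** It asks for cardiac change to be related to disease status, and the two-group test or a regression with a binary predictor could do that. This stands. A reader might infer that goal 2 gets no answer at all, but the documents do not support so strong a statement. What has no planned test is the modification hypothesis that gives goal 2 its meaning.

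**Opposite responses are not claimed.** A reader might infer that pH acts in opposite directions in the two groups and that the effects cancel. The documents say only that the factors might modify the response. The only opposite directions they describe are above and below pH 7.20 in animals. Cancellation is one possibility; the defect needs only different slopes.

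**The 10% rule is legitimate for its purpose.** It screens for confounding, and cardiac disease is not named as a candidate, so it cannot be said that the plan will discard it. This also stands. The defect is the missing product term, and keeping disease as a main effect alone would not repair it.

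**The term may not be estimable, or may be underpowered.** If the Introduction's exclusion applies, few or no patients with known cardiac disease are enrolled. If it does not, power may still be low. Both are real limits on the remedy, but neither shows that the current analysis tests the hypothesis.

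**Conclusion.** The point holds in a limited form. The modification hypothesis attached to a primary goal has no planned test, and any difference in slopes would be averaged into one coefficient. That follows from the text of all three copies of the methods and needs no assumed numbers.

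The size of the consequence does depend on assumptions. The disease share, the slopes and the independence of disease from pH change are all supplied here, and the pooled slope could be slightly or badly misleading. The power of the remedy at 346 patients and a 30% share runs from about 25% to about 98% over the slopes considered. A claim that the term would reliably detect modification is therefore not supported either. The gain is an estimate of each group's slope with its uncertainty.

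**What to change.** **Before any change to the model,** reconcile the Introduction's exclusion of patients with cardiac history with goal 2, Sections 7.1–7.2 and the data form. If the exclusion stands, goal 2 cannot be addressed as a comparison by disease status and should be reworded. If it does not, define underlying cardiac disease from named fields on the form.

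**Then, in Section 8 and its two copies:**

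- Add a change-in-pH by cardiac-disease product term to the pH-effect model as the pre-specified analysis of goal 2, with the disease main effect kept by design.
- Report the pH slope with 95% CI in patients with and without cardiac disease, and the difference with its CI.
- Limit the 10% rule to the other covariates.
- State the expected precision, and that a non-significant product term is not evidence of no modification.

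**Acid-base type** should be secondary and exploratory. Three types need two product terms. It also requires PaCO2 and bicarbonate to be recorded (the form as printed shows no blood-gas fields, though it may be incomplete), a rule for which of the two blood gases defines the type, and reconciliation with the Introduction, which describes a metabolic disorder population.

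**Cost.** For cardiac disease, this is plan wording and one extra model term, since the relevant history is already on the form. For acid-base type, it may mean added data fields. The statistical price is that a slope difference is estimated much less precisely than a common slope.

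### The 10% change rule treats any sufficiently large shift in the pH coefficient as confounding and does not bar variables that pH itself changes, while goal 3 is assigned no step relating its factors to pH

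*Combined protocol and SAP*

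**What the plan says.** Section 8 describes two multivariable linear regressions. The same text appears in the Study Summary and in section 4 (Study design).

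- **Estimative model.** Its purpose is to estimate "the effect of the predictor Change of pH (between the lowest and highest pH) on the response Change in cardiac output". On covariates it says: "The possible role as confounding factors of several variables on this relationship has been evaluated". The variables are not named. The retention rule is: "They remain in the model if they produce a change greater than 10% in the coefficient of the predictor of interest". The plan labels the two outcomes as follows: "presence of confounding bias) and withdraw if the change is less than 10% (absence of confounding bias". The rule is introduced for the multivariate models generally. Only the estimative model has a predictor of interest, so I read it as applying there.
- **Predictive model.** "A predictive multivariate model of linear regression has been performed to evaluate the factors that intervene in the Cardiac Contractility". Selection is by P value alone: "They remain in the model if they are significant and are removed from the model if they are not significant".

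Secondary goal 3 in section 3 (Objectives) reads: "To establish which factors affected by blood pH have an impact on cardiac function".

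The documents give no list of candidate covariates, no rule on when a covariate must be measured relative to the pH change, and no exclusion of variables that respond to pH.

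**The concern.** A covariate can move the pH coefficient for two quite different reasons. It may be a common cause of pH change and cardiac output change, in which case adjusting removes bias. Or it may be changed by pH and in turn act on the heart, in which case adjusting removes part of the effect being estimated. The size of the shift is the same kind of evidence in both cases. The plan recognises only the first.

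This matters here because goal 3 is about variables of the second kind: its wording describes factors that pH affects and that affect cardiac function. The study intends to look at them, and its rule for the model serving primary goal 1 would call them confounders if they were offered as candidates.

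Goal 3 also lacks half of its own question. The predictive model covers the link from factor to heart. No analysis is assigned to the link from pH to factor, so a strong predictor of contractility that has nothing to do with pH would be listed alongside one that does.

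**Working it through.** **The plan's own figure.** Section 4 gives two-sided alpha 5%, power 80% and n = 346 for a correlation. The printed coefficient of 1.5 is not possible for a correlation; 0.15 is the value that gives the stated size:

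n = ((1.960 + 0.842) / atanh(0.15))² + 3 = (2.802 / 0.1511)² + 3 = 346.6, against 346 stated.

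I therefore use a total standardised pH effect of 0.15 and n = 346 below. That calculation is for an unadjusted correlation with contractility; here its effect size is only borrowed for illustration.

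**When the rule keeps a mediator.** Let T be the total effect and s the share passing through one mediator, with no confounding. With the mediator in the model the pH coefficient is T(1 − s); without it, T. The relative change on dropping it is s/(1 − s) if measured against the full model, or s if measured against the reduced one. In expectation the 10% threshold is crossed once s exceeds 1/11 (9%) or 10% respectively.

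**Simulation.** Assumptions not in the documents: standardised variables, one mediator, pH-mediator correlation 0.4, mediated share 30, 50 or 70%. The 10% rule is applied to each sample.

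| Mediated share | Direct effect, 0.15 × (1 − s) | Mediator kept | Mean pH coefficient under the rule | Power of adjusted pH test |
|---|---|---|---|---|
| 30% | 0.105 | about 91% | 0.107 | about 45% |
| 50% | 0.075 | about 99% | 0.076 | about 26% |
| 70% | 0.045 | about 100% | 0.046 | about 13% |

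Leaving the mediator out gives power of about 80%. Repeat runs differ by a point or so. At correlation 0.5 with shares of 20/50/80%, the mediator is kept in 77/98/>99.9% of runs, the mean coefficient is 0.121/0.075/0.029 and power is 52/23/8%.

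**Two controls.**
- *Share zero.* A variable correlated with pH but with no mediating role is kept in 52% of runs at correlation 0.4 and 62% at 0.5. Retention is thus partly sampling noise. The mean coefficient is not shifted (0.151 in the run at 0.5).
- *Opposite sign.* With a mediated share of −30% the direct effect is 0.15 × 1.3 = 0.195. The mean coefficient under the rule is 0.193, above the true total of 0.15.

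**Goal 3, side by side.** The goal needs two links: pH to factor, and factor to cardiac function. The predictive model addresses the second. For the first, section 8 offers only general tools, such as regression for "The relationship between a continuous quantitative response and one or several predictors", and assigns none of them to this goal.

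**The case against.** The strongest reply is that no harm is shown. The candidates are unnamed, and no text puts a pH-dependent variable among them. Goal 3's factors may be meant only for the predictive model. The data form printed under section 20 lists mainly admission items, diagnosis groups, chronic diseases and APACHE II, which are largely suitable candidates. This stands to the extent that over-adjustment is conditional. A reader might infer that mediators are in fact adjusted away, and the documents do not support that. The form does not settle the matter in the plan's favour either: as reproduced it has no pH or cardiac output field, so it cannot be the whole data set.

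Four other strong readings also go too far:

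- *The bias is always towards no effect.* This holds only if the mediated path has the same sign as the total effect. The Study Summary's hypothesis describes animal data in which cardiac output rises as pH falls to 7.20 and is reduced below it, so the sign cannot be assumed.
- *The planned 80% power is lost.* The sample size concerns an unadjusted correlation with contractility, which the 10% rule does not touch. Only the adjusted pH test is affected.
- *Goal 3 cannot be analysed.* Correlation and regression could relate a factor to pH; what is missing is their assignment to the goal.
- *Particular haemodynamic or electrolyte variables will be entered.* The documents name none as candidates.

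Finally, restricting candidates to baseline items would have its own cost. The exposure is a change between two moments, so time-varying common causes could be left out. This stands, and the fix allows for it.

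**Conclusion.** The concern holds in conditional form. The plan's criterion cannot separate a confounder from a variable on the path from pH to the heart, no safeguard keeps the latter out, and goal 3 makes such variables objects of study. If one carrying a substantial share of the effect is offered, the rule will usually keep it, and the coefficient will be reported as corrected for confounding when it is only the remaining part of the effect. The error is downwards or upwards according to the sign of the path.

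The sizes above are illustrative. They rest on an assumed total effect of 0.15, an assumed pH-mediator correlation and assumed mediated shares. The qualitative result rests on none of these.

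Separately, goal 3 as assigned can list predictors of contractility unrelated to pH. Both points should be corrected before analysis, since they bear on the interpretation of the adjusted pH estimate and on a stated secondary goal.

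**What to change.** **Estimative model.** Before analysis, name the candidates for the 10% rule and limit them to variables that precede, or are not caused by, the pH change:
- baseline items such as age, sex, diagnosis group and chronic disease;
- a severity score only if scored before the pH change;
- recorded time-varying common causes of pH and cardiac output.

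Bar variables affected by pH from the model meant to give the total effect.

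**Goal 3.** State two steps:
1. Regress the change in each factor on the change in pH.
2. Regress the change in cardiac function on the change in pH, with and without that factor, and report both pH coefficients with confidence intervals as exploratory.

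Make the change in the Study Summary, section 4 and section 8, which carry the same text.

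**Cost.** Revised wording and a few extra regressions, with no effect on patients or recruitment. Step 1 needs each factor recorded at the two moments that define the pH change, so confirm that the data collection covers this. Someone must also judge which time-varying variables are causes and which are consequences of the pH change, and some residual confounding may remain.

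### The 10% rule for the adjusted pH effect states no reference coefficient and no limit on total drift, so weak confounders acting mostly in one direction can be removed one by one

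*Combined protocol and SAP*

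**What the plan says.** Section 8 (Statistical Methods) describes two multivariable linear regressions. The same text stands in the Study Summary and in Section 4.

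- **Estimative model.** The response is change in cardiac output and the predictor of interest is change of pH, both between the lowest and highest pH. On adjustment the plan says only: "The possible role as confounding factors of several variables on this relationship has been evaluated". The variables are neither named nor counted.
- **Predictive model.** It looks for factors that bear on cardiac contractility.

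The procedure is shared: "Both the predictive and the estimative models have been carried out with the manual backward step procedure". Covariates come up for removal in a sequence set by their P values.

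The retention rules differ. For the predictive model: "They remain in the model if they are significant and are removed from the model if they are not significant". The other rule is: "They remain in the model if they produce a change greater than 10% in the coefficient of the predictor of interest". A change below 10% leads to withdrawal and is labelled as showing no confounding bias. The plan calls this a matter of clinical significance and applies it "to decide on the maintenance or withdrawal of the predictors in each step". The sentence introducing this rule speaks of multivariate models generally, but a predictor of interest and a concern with confounding fit only the estimative model.

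The plan does not state the coefficient against which the 10% is measured, a limit on total change, a fixed adjustment set, a fully adjusted comparison, or any allowance for selection in the final P values.

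**The concern.** A change under 10% at one step does not show that a covariate is not a confounder. If each step is compared with the one before, small changes in the same direction compound. As a worst-case illustration, ten removals of 9% each give 1.09^10 = 2.37, although no single step breaks the rule.

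This is the only explicitly described confounder-adjusted model of the pH effect, and it bears on primary goal 1 (Section 3). ICU patients differ in diagnosis, severity and comorbidity, all of which may relate to both pH and cardiac output. At stake are the size of the reported pH effect and the error rates of its P value. The predictive model raises a related issue: its predictors are chosen on P < 0.05 and then reported with P values that treat the model as fixed.

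**Working it through.** **1. Sample size and effect size.** Section 4 gives two-sided alpha 5%, power 80% and N = 346. The usual formula for a correlation is n = [(z₀.₉₇₅ + z₀.₈₀)/atanh(r)]² + 3. With r = 0.15: [(1.960 + 0.842)/0.1511]² + 3 = 346.6, which reproduces 346. The printed coefficient, 1.5, is impossible for a correlation. I therefore used n = 346 and a true standardised slope of 0.15. That figure is borrowed: Section 4 sizes the study on cardiac contractility, not cardiac output.

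**2. Number of candidates.** The plan gives none. From the data form and Section 1, a plausible set is 11 admitting diagnosis groups (10 coefficients), seven ICUs (6), and age, sex, admission type, APACHE II and chronic cardiac disease (5): 10 + 6 + 5 = 21. I assumed 20.

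**3. Simulation of the rule.** Assumptions not in the documents: independent standard-normal covariates; residual SD 1; each confounder has the stated strength both as its correlation with change in pH and as its slope on the outcome; the remaining candidates are noise. Elimination starts from the full model, least significant covariate first. A covariate goes if the pH coefficient moves by no more than 10%. Coverage refers to ordinary 95% intervals from the final model.

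| Scenario (true slope 0.15, 20 candidates) | 10% measured from | Mean estimate | Coverage |
|---|---|---|---|
| 8 confounders of 0.10, same direction | previous step | 0.19 | 75–79% |
| 10 confounders of 0.12, same direction | previous step | 0.22 | 60–61% |
| 8 of 0.10, pulling against the pH effect | previous step | 0.12 | 96% |
| Half in each direction | previous step | 0.15 | 93–94% |
| Same-direction scenarios | full model | – | about 91% |
| All 20 covariates kept | – | 0.15 | 94–96% |

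Ranges reflect separate runs; Monte Carlo error is one to two points. When the confounders pull against the pH effect, power is 52%, against 69% for the full model.

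**4. Second simulation, with every candidate a true confounder** (strength 0.10, 1,500 replicates, previous-step rule):

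- Ten confounders, slope 0.15: mean 0.207, that is (0.207 − 0.15)/0.15 = +38%; coverage 67.9%. On average 2.3 of the ten are kept. The full model gives 0.149 and 94.2%.
- Five confounders, slope 0.15: mean 0.179 (+19%), coverage 83.9%.
- Ten confounders, slope 0: type I error 7.9%, against 5.9% for the full model in the same run.
- Ten covariates unrelated to pH (no confounding), slope 0.15: mean 0.148, coverage 95.2%.
- Ten confounders, slope 0.15, 10% measured from the full model: mean 0.160 (+7%), coverage 90.9%.

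**5. Bias or interval width?** With ten same-direction confounders the reported SE averages 0.057 against an empirical SD of 0.086, so the estimate is biased and the interval too narrow. With confounders pulling against the effect the SE is 0.056 against an SD of 0.043: the estimate is attenuated and the interval too wide.

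**6. Cost of keeping everything.** The full-model SE is 0.058–0.060, against 0.056–0.058 after selection. The ratios are 0.058/0.056 = 1.036 and 0.060/0.058 = 1.034.

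**7. Predictive model.** If all m candidates were noise and independent, the chance that at least one is significant is about 1 − 0.95^m. For m = 25 this is 1 − 0.277 = 72%; simulated backward selection gives 75% (54% for m = 15, 86% for m = 35). The plan does not give m.

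**The case against.** The harm is conditional. It needs several weak confounders that mostly act in one direction. With mixed signs the rule does about as well as the full model. Strong confounders are kept: with two of strength 0.30 the mean was 0.147 and coverage 94%. Decisions made at each step do not by themselves fix the reference coefficient. If it is the full model, drift is held near 10% and the undercoverage is modest. All of this stands and limits the point.

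Four stronger readings are tempting, and the documents do not support them.

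- *The intervals will be too narrow.* This fails when confounders pull against the pH effect, and part of the undercoverage elsewhere is bias rather than width. The plan also states no confidence intervals for these models; a 95% confidence level appears only in the sample size text.
- *This is the study's main effect estimate.* The plan does not call it that. Section 4 frames the primary objective around contractility, whereas this model's response is cardiac output.
- *The list of contractility factors will contain noise.* That depends on how many candidates there are and how many are null, which the plan does not say.
- *Full adjustment gives the right answer.* It does in the simulations because they contain no unmeasured confounding. They do not show that the variables collected here suffice.

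What remains is that the rule, on its most natural reading, allows cumulative drift, and that nothing in the plan would reveal it.

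**Conclusion.** The concern holds in conditional form. The elimination rule for the adjusted pH effect is underspecified, and read as a change from the previous step it can move the estimate well beyond the 10% it appears to guarantee. At the planned size and a true slope of 0.15, the inflation is roughly 25–45% (0.19/0.15 = 1.27; 0.22/0.15 = 1.47) under same-direction confounding. The attenuation is about 20% (0.12/0.15 = 0.80) under opposing confounding. These sizes rest on the assumed number, strength and independence of the confounders, and on reading the removal order as least significant first. P values, and any intervals reported, ignore the selection on every reading, though the practical effect ranges from negligible to serious. The plan should be changed before analysis, because the better method is available at almost no loss of precision.

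**What to change.** **Estimative model.** Name the adjustment set in advance and keep all of it:

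- age, sex, admission type, admitting diagnosis group and APACHE II, all on the data form;
- site, taken from the code in the study ID (Section 11), since the form as reproduced shows no ICU field; check that the code separates the seven ICUs;
- chronic cardiac disease, once the exclusion of patients with cardiac history in Section 1 has been reconciled with primary goal 2, which compares patients with and without cardiac disease.

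Keep the 10% rule, if wanted, only as a sensitivity analysis with the change measured cumulatively from the full model. Report both estimates.

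**Contractility model.** Report the full model beside the selected one. Repeat the whole selection in bootstrap samples, give the frequency with which each predictor is retained, and describe the retained factors as exploratory.

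**Cost.** A change of wording in Section 8 and its two copies, and one bootstrap run. No new data or patients are needed. The price is about 20 parameters in a model of about 346 patients, with a standard error 3–4% larger in the simulations.
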